Secondary Endpoint(s)	
 
Change from baseline in the blood (serum) and esophageal TGF-<math>\beta</math> levels in participants receiving losartan potassium at the EOT visit (or at early withdrawal) as determined by research blood samples and EGD with biopsy, respectively.
 
Normalization of the EoE transcriptome in participants receiving losartan at the EOT visit (or at early withdrawal) as determined by EGD with biopsy.
 
Change from baseline in histopathology in participants receiving losartan potassium at the EOT visit (or at early withdrawal) as determined by EGD with biopsy.
 
Change from baseline esophageal compliance in participants receiving losartan at the EOT visit (or at early withdrawal) as determined by EndoFLIP.
 
Change from baseline PFC (Pediatric Eosinophilic Esophagitis Symptom Severity [PEESS], PedsQL Eosinophilic Esophagitis Module [PedsQL™ EoE], EoE Quality of Life Questionnaire, and EEsA) in participants receiving losartan at the EOT visit (or at early withdrawal) as determined by EndoFLIP.
 

Accrual Objective	
 
It is estimated that 30 patients will need to be screened for a total of approximately 15 participants enrolled in the study. Of the 15 participants enrolled, at least one third will have evidence of EoE with CTD, whereas the remaining participants will have no evidence of a CTD.
 

Study Duration	
 
Total duration of treatment is approximately 16 weeks. During the titration phase, participants will be on titrated doses of losartan for 4 weeks. During the maintenance phase, participants will be on a stable dose of treatment for 12 weeks.
 

Treatment Description	
 
• During the study oral administration of losartan tablets or suspension occurs once a day, at about the same time each day, throughout the treatment period. The dose of the study agent to be administered will depend on the participant's body weight and will be calculated (mg/kg) on the basis of a titration schedule during the treatment (i.e., titration and maintenance) phase, not to exceed the daily dose of 100 mg. The medication dosage for losartan potassium will change throughout this study, titrating to a higher dose.
 

------------------------------	---

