### 12.5 Sample Size Considerations

Five patients with EoE-CTD and 10 patients with EoE will be recruited into the study. Since this represents a pilot study to evaluate whether the treatment affects endpoints, the sample size was not selected on the basis of power considerations for statistical testing. The estimates of treatment effect from this study will be used to power future studies. Based on historical data from the [REDACTED], it is estimated that the standard deviation of the change from baseline at 12 weeks based on the square root transformation of the eosinophil/HPF values will be approximately 5. Table 7 provides the width of the two-sided 95% confidence interval for the change from baseline in eosinophil/HPF for various scenarios of sample size and standard deviation.

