Additionally, to evaluate the effect of losartan on the reduction of esophageal eosinophils in participants with EoE (with or without a CTD), we will use paired non-parametric Wilcoxon Rank sum test. The Wilcoxon rank sum paired test will be used given the small sample size and the broad range of eosinophils which could be present in our participants. Analyses will be performed using the whole cohort and stratified by CTD. Statistical significance will be set at $\alpha = 0.05$. This corresponds to testing the following hypothesis:

H0: baseline and study completion are equal vs. H1: baseline and study completion are not equal.

Analyses of Secondary Endpoint(s)/Outcome(s)

To assess changes over time for continuous secondary and safety outcomes, a mixed effects model for repeated measures analysis will be used. The dependent variable will be the change from baseline. The “participant nested within group” term will be considered a random effect. Time (i.e. measurement time) will be included as a continuous effect. Terms in the model will be time, group (i.e., EoE and EoE-CTD), and time-by-group interaction. The baseline value will be used as a covariate in the model. If necessary, to meet the assumptions of the analysis, an appropriate transformation will be used (e.g., square root, log, rank). The hypotheses that will be tested are whether there is a significant trend over time and whether this trend is consistent between the CTD and non-CTD groups (i.e. testing the interaction term). If the trend is not consistent between groups based on the statistical test at $\alpha=0.10$, we will estimate the trend within each of the two groups by including terms in the statistical model that estimates the trend within each group and the hypothesis to be tested within each group is whether this trend is significantly different than zero. We will systematically assess the residuals to determine whether a linear or quadratic model best fits the data. In statistical terms, the hypotheses are provided below.

For testing consistency of the time trend (β) between the CTD and non-CTD group, the hypotheses are:

H0: $\beta_{\text{EoE-CTD}} = \beta_{\text{EoE (non-CTD)}}$ vs. H1: $\beta_{\text{EoE-CTD}} \neq \beta_{\text{EoE (non-CTD)}}$.

For testing linear trend combining across groups (if there is consistency of the time trend):

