H0: $\beta=0$ vs. H1: $\beta\neq 0$ where β is the slope of the line across groups. Similar hypotheses will be tested if analysis of the residuals indicates that higher order terms need to be included in the model (e.g. quadratic). If there is strong evidence that the time trend is not consistent between the two groups, we will test the above hypothesis within each of the two groups. In addition, the two-sided, 95% confidence interval for the slopes will be calculated to provide estimates of the slope for future studies.

The percentage of participants for whom peak eosinophil counts are < 15 eosinophil/HPF at Week 16 will be estimated within each CTD group along with a 95% confidence interval.

Safety endpoints that are categorical will be summarized within each group. Further, any SAEs or Grade 3 or above will be reported descriptively.

Software Used (with References) and Specialized Macros (with References)

SAS version 9.4, JMP 14.

This SAP has been reviewed and approved by:

Investigator

Date

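### Within-group trends for repeatedly measured secondary and safety outcomes are estimated only after a significant interaction test at 0.10, and with 5 v 10 participants a non-significant test is weak evidence that the groups agree.

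*SAP*

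**What the plan says.** The SAP, under Analyses of Secondary Endpoint(s)/Outcome(s), models change from baseline with time (continuous), group, time-by-group and the baseline value, with participant as a random effect. Protocol 12.4 has the same text. The interaction test decides what follows: "If the trend is not consistent between groups based on the statistical test at" α = 0.10, a separate trend is estimated and tested for each group. The combined slope is tested if the trends are consistent.

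Two later sentences in both documents blur this rule. One restates the trigger as strong evidence of inconsistency and gives no level. The other says that a 95% "confidence interval for the slopes will be calculated to provide estimates of the slope for future studies". It does not say whether these are group or pooled slopes, or whether they depend on the test.

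Other group results are unconditional. The primary change is estimated within each group and combined. The percentage below 15 eosinophils/HPF is given by group with an interval, and categorical safety endpoints are summarized by group.

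On size, Protocol 12.5 states: "Five patients with EoE-CTD and 10 patients with EoE will be recruited into the study". The Synopsis makes five a minimum share: "Of the 15 participants enrolled, at least one third will have evidence of EoE with CTD". Protocol 12.5 adds that "the sample size was not selected on the basis of power considerations for statistical testing" and that the estimates of treatment effect will be used to power later studies.

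**The concern.** The rule lets a significance test decide whether an estimate is produced at all, in a study that its own protocol says was not sized for testing. A non-significant interaction is read as agreement between the groups. With five participants in one group, it may only mean that the test could not see a difference.

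Two things are at stake. A real difference between EoE and EoE-CTD in symptom scores or repeated safety measures could be pooled over, with no group estimate left for planning. And group estimates that do appear have been selected for looking different, so they overstate the contrast. Neither document explains why these outcomes are handled differently from the primary endpoint, which is reported both ways without a test.

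**Working it through.** **The plan's own figures.** The documents give no power for the interaction test. The nearest design figure is Protocol Table 7, the half-width of a 95% interval: t(0.975, n−1) × SD/√n. With SD 5 this gives 2.77, 3.58 and 6.21 for n = 15, 10 and 5, and with SD 10 it gives 5.54, 7.15 and 12.42. All six entries match after rounding.

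**Where the gate can act.** Protocol Table 4 schedules endoscopy with biopsies, EndoFLIP and research laboratory samples at screening and end of treatment only. Change from baseline then has a single value per participant, so neither a slope nor a time-by-group term can be estimated. Vital signs and clinical laboratory samples recur at weeks 4, 8, 12 and 16. The questionnaires do too, and also at week 20.

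**Inputs.** Group sizes 5 and 10 (Protocol 12.5); two-sided α = 0.10 (SAP). The group difference d, in SD units, is an assumption. The only SD given ("will be approximately 5") is for square-root eosinophil counts, not for any secondary outcome.

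**Simple approximation: one slope or change per participant, two-sample t.** Degrees of freedom 13, critical value 1.771, noncentrality d/√(1/5 + 1/10) = d/0.548.

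| True difference | Noncentrality | Gate opens | Gate stays shut |
|---|---|---|---|
| 0.5 SD | 0.91 | 22% | 78% |
| 1 SD | 1.83 | 53% | 47% |
| 1.5 SD | 2.74 | 83% | 17% |

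For 1 SD, splits of 6 v 9 and 7 v 8 open the gate 56% and 57% of the time. Power of 80% needs 1.44 SD.

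**Closer to the planned model: random intercept, linear time.** Here 1 SD means that the groups diverge linearly and differ by 1 SD at week 16, so the slope difference is 1/16 per week. With within-participant correlation ρ, the standard error is √[(1−ρ)/Sxx × (1/5 + 1/10)]. For weeks 4, 8, 12 and 16, Sxx = 36 + 4 + 4 + 36 = 80 and the degrees of freedom are 60 − 15 − 2 = 43. Adding week 20 gives Sxx = 160 and 75 − 15 − 2 = 58, if the divergence continues after treatment ends.

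| ρ | Miss rate, weeks 4–16 | Miss rate, week 20 added |
|---|---|---|
| 0.3 | 67% | 48% |
| 0.5 | 59% | 35% |
| 0.7 | 42% | 17% |
| 0.9 | 6% | about 0% |

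For example, with ρ = 0.5 and visits to week 16, the standard error is √(0.5/80 × 0.3) = 0.0433. The noncentrality is 0.0625/0.0433 = 1.44, and power is 41%.

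**Selection.** I simulated the simple approximation and kept only trials in which the gate opened. The mean absolute difference was about 1.19 SD for a true 0.5 SD (1.19/0.5 = 2.4 times) and about 1.39 SD for a true 1 SD (1.4 times).

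**Width without the gate.** In SD units the 95% half-widths are 2.776/√5 = 1.24 for n = 5, 2.262/√10 = 0.72 for n = 10, and 2.160 × 0.548 = 1.18 for the difference.

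**The case against.** The best defence is that this is a prespecified rule, at a relaxed level, in a study described as preliminary and descriptive. The primary endpoint is already reported by group and pooled. Protocol 12.5 speaks of treatment-effect estimates for future studies without promising group-level estimates of secondary outcomes. The sentence on slope intervals is plural and carries no condition, so it may already intend ungated group intervals. All of this limits the weight of the point. None of it makes a non-significant interaction with 5 v 10 participants evidence of consistency. If ungated intervals are intended, the text should say so, because it currently also makes within-group estimation conditional.

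Three stronger readings are tempting, and the documents do not support them.

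- A reader might infer that every group-specific secondary result is gated. The percentage below 15 eosinophils/HPF and the categorical safety summaries are not.
- A reader might infer that the gate hides a 1-SD difference about half the time. That figure comes from a two-sample t-test on one value per participant, not from the planned slope test. For the latter it depends on a correlation that no document gives.
- A reader might infer that group estimates are lost in most realistic cases. No document says what difference is realistic. Even the simple approximation opens the gate 53% of the time at 1 SD and 83% at 1.5 SD.

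**Conclusion.** The point holds for within-group trends in continuous outcomes with repeated post-baseline measures, in practice the questionnaires and repeated safety measures. For an assumed 1-SD difference the chance of pooling over it is about 47% in the simple approximation. In the random-intercept model it is about 6% to 67% with visits to week 16, and about 0% to 48% with week 20, for correlations from 0.9 down to 0.3. The exaggeration of about 1.4 times applies to a true 1 SD in the simple approximation. The effect size and the correlations are assumptions.

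The argument does not depend on any one of these figures. An estimate for planning should not depend on a test that the study was not sized for, and the two triggers and the unspecified slope intervals need clarifying in any case. This is a reporting improvement. It leaves the primary analysis untouched.

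**What to change.** In the SAP section on secondary endpoints and in Protocol 12.4:

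- Remove the 0.10 condition and the strong-evidence restatement.
- For repeatedly measured outcomes, always report the EoE, EoE-CTD and combined slopes with 95% intervals, plus the between-group difference with its interval. Keep the interaction p-value as descriptive.
- State that the intervals for the slopes cover all of these and are unconditional.
- State whether week 20, after treatment ends, enters the slope.
- For outcomes measured only at screening and end of treatment, report the change at end of treatment by group and pooled, with intervals, instead of a slope.

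The cost is wording and a few table rows, with no change to data collection. The intervals for five participants will be wide, about ±1.24 SD. Table 7 already accepts that width for the primary endpoint (±6.2 with SD 5, and 6.2/5 = 1.24).

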### 3. Primary Endpoint(s)/Outcome(s)

- Change from baseline in the peak esophageal eosinophil count in participants receiving losartan potassium at the end-of-treatment (EOT) visit (or at early withdrawal) as determined by esophagogastroduodenoscopy (EGD) with biopsy and reported as eosinophils per high-power field (eosinophils/HPF).
- A primary safety endpoint is also included to monitor for adverse events in the enrolled subjects. Specifically, as a descriptive investigation, any SAE or Grade 3 and above AEs that arise during the conduct of this pilot study will be reported.

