#### 5. Premature Discontinuation of Investigational Agent

Study therapy may be prematurely discontinued for any participant for any of the following reasons:

- Occurrence of an AE that, in the opinion of the investigator, requires the participant's permanent withdrawal from the study agent. In the event of withdrawal from the study agent due to the occurrence of a SAE, the Investigator and Sponsor must be notified within 24 hours (See section 11.7). A participant withdrawn secondary to an ongoing SAE that is considered possibly or probably related to the study agent must be followed clinically until resolution or stabilization of the SAE.
- Insufficient therapeutic effect requiring alternative or additional therapy for the treatment of EoE, including the need for "rescue" systemic or swallowed inhaled corticosteroid therapy, in addition to the study agent, for the treatment of the current EoE. Criteria for withdrawal due to lack of efficacy will rely on the best clinical judgment of the PI that the participant requires a new therapeutic intervention due to the clinical state of his/her EoE. Examples would include: worsening of the presenting predominant symptom of EoE, the emergence of a new additional symptom of EoE that is at least moderate in intensity and is due to EoE, or the need for new systemic treatment (e.g., oral corticosteroids). In contrast, small dietary modifications or modest increases in symptom frequency without increased severity would not constitute withdrawal criteria.
- Study therapy may also be prematurely discontinued for any participant if the investigator believes that the study treatment is no longer in the best interest of the participant.

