### 3. Participant Replacement

Enrolled participants who receive the study agent and prematurely discontinued or withdraw from the study will be replaced if they do not reach Week 16 of the study, including the EOT visit (EGD). Additional participants will be enrolled in the same manner as all other participants. Participant numbers will not be re-used. Any enrolled participant will be included in the intent-to-treat analysis.

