For testing consistency of the time trend ( $\beta$ ) between the CTD and non-CTD group, the hypotheses are:

$H_0: \beta_{EoE-CTD} = \beta_{EoE(non-CTD)}$  vs.  $H_1: \beta_{EoE-CTD} \neq \beta_{EoE(non-CTD)}$ .

For testing linear trend combining across groups (if there is consistency of the time trend):

$H_0: \beta=0$  vs.  $H_1: \beta \neq 0$

where  $\beta$  is the slope of the line across groups. Similar hypotheses will be tested if analysis of the residuals indicates that higher order terms need to be included in the model (e.g. quadratic). If there is strong evidence that the time trend is not consistent between the two groups, we will test the above hypothesis within each of the two groups. In addition, the two-sided, 95% confidence interval for the slopes will be calculated to provide estimates of the slope for future studies.

The percentage of participants for whom peak eosinophil counts are  $< 15$  eosinophil/HPF at Week 16 will be estimated within each CTD group along with a 95% confidence interval.

Safety endpoints that are categorical will be summarized within each group. Further, any SAEs or Grade 3 or above will be reported descriptively.

All analyses will be performed using SAS version 9.2 or later (Cary, NC).

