This is a phase II, open-label trial of losartan in patients diagnosed with EoE with or without a CTD. Prior to entry, patients must meet the current consensus criteria for EoE in which efforts are made to rule out other causes of esophageal eosinophilia. The trial will perform a preliminary assessment of the effect of the maximum tolerated dose of losartan in participants with active EoE as determined by the absence of side effects and by vital signs being within normal limits. The primary endpoint of the study is the reduction in the number of esophageal eosinophils in participants who will receive losartan orally once a day (Figure 1). The primary safety endpoint is descriptive and will require reporting of SAE or Grade 3 and above AEs.

Figure 1 Study Design Flowchart

Analysis Populations

The analysis population for the primary and secondary endpoints will be participants who received Losartan and maintained the baseline EoE treatment throughout the course of the study.

Statistical Considerations and Analytical Plan

Overview

Change from baseline for eosinophil counts will be calculated for each participant. The average change from baseline within each group and combining both groups (i.e. EoE and EoE-CTD) will be calculated along with the corresponding two-sided, 95% confidence interval. Additionally, we will perform paired tests which will specifically test whether there was significant change between baseline and study completion. The last observation carried forward (LOCF) method will be used for participants who end the trial early. To assess changes over time for continuous secondary and safety outcomes, a mixed effects model for repeated measures analysis will be used. Unless stated otherwise, all statistical testing will be done at $\alpha=0.05$.

Variables of Interest

Primary outcome:

- 1) Change in eosinophils/hpf from baseline to post treatment
- 2) Rate of SAE / Grade 3 or above AE

Secondary outcomes:

- 1) Blood (serum) and esophageal TGF- β levels
- 2) EoE transcriptome
- 3) Histopathology as assessed by the Histology Scoring System (HSS): Will include the overall score, grade score, stage score, and the inflammatory and structural sub-scores. Scores will be reported as distal, proximal, and maximum
- 4) Esophageal compliance as measured by EndoFLIP.
- 5) PROS (Pediatric Eosinophilic Esophagitis Symptom Severity [PEESS], PedsQL Eosinophilic Esophagitis Module [PedsQLTM EoE], EoE Quality of Life Questionnaire, and EEsAI)

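### The denominator and the scoring of early leavers for the <15 eos/HPF response are not settled: the SAP population drops treatment failures who start other EoE therapy, while the protocol keeps them

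*SAP*

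**What the plan says.** **Response.** The SAP (Analyses of Secondary Endpoint(s)/Outcome(s)) reads: "The percentage of participants for whom peak eosinophil counts are < 15 eosinophil/HPF at Week 16 will be estimated within each CTD group". Protocol 12.4 matches it: "eosinophil/HPF at Week 16 will be estimated within each CTD group along with a 95% confidence interval".

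**Primary eosinophil endpoint.** Protocol 3.3 takes it "at the end-of-treatment (EOT) visit (or at early withdrawal"). The response sentence has no such clause.

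**Early leavers.** The Overviews of both documents, and both primary analyses, state: "The last observation carried forward (LOCF) method will be used for participants who end the trial early". In the Overviews this is not tied to an endpoint. It is not repeated beside the response sentence. The model for other secondary outcomes does not reach a binary response: "To assess changes over time for continuous secondary and safety outcomes, a mixed effects model for repeated measures analysis will be used".

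**Who is counted.** Protocol 10.3 puts any enrolled participant in the intent-to-treat analysis. The SAP (Analysis Populations) restricts the primary and secondary endpoints to those who took losartan and held their baseline EoE treatment for the whole study.

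**Exits and replacement.** Among the reasons for stopping, protocol 6.5 lists "Insufficient therapeutic effect requiring alternative or additional therapy for the treatment of EoE". Under 10.3, dosed participants who leave early "will be replaced if they do not reach Week 16 of the study, including the EOT visit (EGD").

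**Exit biopsy.** Section 8.8 asks for it within one week of the last dose, and the Table 4 footnote on early withdrawal within two weeks. Section 10.4 places all EOT procedures at the time of withdrawal.

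**The concern.** A response rate from a single-arm, open-label study has no control group to absorb a selection effect, so its denominator has to be fixed in advance. Treatment failures ought to lower the rate. Here, depending on which document is followed, a failure either stays in, or is removed and replaced by a new participant.

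The groups are planned at 5 and 10, so the handling of one person shifts the estimate visibly. This is also the one responder percentage with its own analysis sentence, and it is the example used for the precision table (Table 8). Protocol 12.5 says the study's treatment-effect estimates will be used to power later studies. If the scoring is chosen once the biopsies are known, the rate is hard to defend.

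**Working it through.** **1. What each reading does with an early leaver**

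Biopsies are scheduled only at screening and at EOT/early withdrawal (Table 4). Entry requires at least 15 eos/HPF, so a baseline value carried forward is always a non-response.

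| Early leaver | SAP population | Protocol ITT with LOCF |
|---|---|---|
| Stops for lack of effect, starts other EoE therapy | Out of the denominator; replacement enters | Kept; scored as in the rows below |
| No exit biopsy, baseline treatment unchanged | Kept if LOCF covers this endpoint: non-responder | Non-responder |
| Exit biopsy ≥15 | Kept if treatment unchanged: non-responder | Non-responder |
| Exit biopsy <15 | Kept if treatment unchanged: responder if LOCF applies | Responder, even if new therapy began before the biopsy |

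If the Week 16 wording is taken literally and LOCF is not applied, every early leaver lacks a value and drops out.

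**2. Reproducing the plan's intervals**

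The score (Wilson) interval, with p = x/n and z = 1.96, is

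[p + z²/(2n) ± z·√(p(1−p)/n + z²/(4n²))] / (1 + z²/n).

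For 2/5: centre (0.400 + 0.384)/1.768 = 0.443; half-width 1.96·√(0.0480 + 0.0384)/1.768 = 0.326; interval 11.8% to 76.9%. Table 8 gives 12% to 77%. All six within-group rows of Table 8 reproduce (n = 10: 49.0–94.3, 31.3–83.2, 16.8–68.7; n = 5: 37.6–96.4, 23.1–88.2, 11.8–76.9). The combined-group row at 40% does not (19.8–64.3 against 28–64). That is a separate matter and does not affect this point, because the response is estimated within each group.

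**3. Illustrations**

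The documents give no withdrawal rate. The numbers of leavers and responders below are assumptions, with the observed rates near the lowest response rate in Table 8 (40%). Each leaver is taken to be a lack-of-effect exit who changes EoE therapy.

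| Group and case | SAP population | All dosed, leaver a non-responder | Gap |
|---|---|---|---|
| EoE-CTD, 1 leaver replaced, 2 responders | 2/5 = 40% (12–77%) | 2/6 = 33% (10–70%) | 7 points |
| EoE-CTD, 1 leaver not replaced, 2 responders | 2/4 = 50% (15–85%) | 2/5 = 40% (12–77%) | 10 points |
| EoE, 2 leavers replaced, 4 responders | 4/10 = 40% (17–69%) | 4/12 = 33% (14–61%) | 7 points |
| EoE, 2 leavers not replaced, 4 responders | 4/8 = 50% (22–79%) | 4/10 = 40% (17–69%) | 10 points |

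The direction does not depend on these assumptions. Removing d ≥ 1 non-responders from x/n gives x/(n−d), which exceeds x/n whenever x > 0.

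Under protocol ITT with LOCF, if the EoE-CTD leaver has an exit count below 15, the rate becomes 3/5 = 60% (23–88%) without replacement, or 3/6 = 50% (19–81%) with it.

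**4. Can someone withdrawn for lack of effect have an exit count below 15?**

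Yes. The criteria in 6.5 are symptoms and clinical judgement, not histology, and protocol 1.1 itself notes that biopsy findings and symptoms often disagree. Nothing in the plan requires the exit biopsy to come before new therapy.

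**The case against.** The strongest reply is that the plan already deals with early leavers. LOCF stands unrestricted in both Overviews, an exit biopsy is planned, and the protocol has an ITT sentence. The heading of 8.8 and the Visit 6 column of Table 4 join EOT and early withdrawal under Week 16, so the response timepoint may be only a visit label. The percentage is not among the listed primary or secondary outcomes, carries no hypothesis, and sits in a pilot not sized on power.

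Much of this stands, and it rules out three stronger readings that a reader might infer:

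- **That no rule scores early leavers.** The unrestricted LOCF sentence can be read to cover this endpoint, and protocol 10.3 answers the denominator question for the protocol.
- **That every reading inflates the rate.** With LOCF, a leaver without an exit biopsy carries forward at least 15 eos/HPF and is a non-responder, exactly as under the fix below. An exit count below 15 without new therapy is an observed histologic response, though after shorter exposure.
- **That a participant given new EoE therapy can be a responder under the SAP.** The SAP population excludes that person. The 3/5 and 3/6 cases arise only under protocol ITT with LOCF. Section 10.4 puts the EOT procedures at the time of withdrawal, so a biopsy after new therapy is possible but not something the plan sets out.

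The reply does not remove the conflict between the two populations. Section 10.3 also uses Week 16 as elapsed time on study, so the visit-label reading is available but not secure. And the SAP, followed as written, takes out precisely the participants whose treatment failed and needed other therapy.

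**Conclusion.** The point holds as a conflict between the documents together with an unclear scoring rule. Under the SAP population the <15 eos/HPF rate is biased upward relative to all treated participants whenever someone stops for insufficient effect and changes EoE therapy; replacement fills the place but does not restore the failure to the denominator. Under protocol ITT with LOCF that person is kept, and is a non-responder unless an exit biopsy, possibly taken after new therapy, shows a count below 15.

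The size is illustrative because no withdrawal rate is stated: about 7 points with replacement and 10 without, for one such leaver in EoE-CTD or two in EoE. The example intervals overlap heavily, so this concerns what the rate means and its direction of error, not a change in significance. It should be settled before analysis, but it does not threaten the primary analysis of change in count.

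**What to change.** Add one paragraph to the SAP and to protocol 12.4 for this endpoint:

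- **Denominator:** every participant who took losartan, including those later replaced, stated as overriding the SAP's restriction to unchanged baseline treatment. This differs from the protocol's ITT set only for anyone enrolled but never dosed.
- **Responder:** peak count below 15 eos/HPF at the EOT biopsy, with no added or increased EoE therapy before that biopsy.
- **Non-responder:** anyone else, including all who stop early and all without an EOT biopsy.
- **Sensitivity analysis:** the observed-biopsy/LOCF rate, with exit biopsies included.

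Separately, reconcile protocol 10.3 with the SAP's Analysis Populations, and the exit-biopsy timing in 8.8 with the Table 4 footnote.

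The cost is a few sentences and no new data. The downside is a slightly lower reported rate, because people who leave for unrelated reasons also count as failures; the sensitivity analysis shows how much that matters.
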